In 2016 Holmes and colleagues (Holmes et al., 2016) introduced a brief imagery-based cognitive intervention (ImCT) for patients suffering from bipolar disorder, using techniques aimed at both, quality of the imagery and appraisals of the imagery. ImCT is a promising intervention as it allows for flexible fine-tuning to target specific elements of imagery. ImCT incorporates an elaborate micro-formulation of imagery (teasing out both

qualitative aspects of imagery as well as appraisals), followed by metacognitive intervention, imagery rescripting or positive imagery and competing task (or a combination of these), tailoring the intervention depending on the outcome of the micro formulation. Holmes and colleagues (Holmes et al., 2016) conducted a pilot study using a non-concurrent baseline design, with a series of A-B replication. Fourteen patients with bipolar disorder were randomly assigned to 4, 5, or 6 weeks baseline after which they received ImCT (in total 10 to 14 sessions). Outcome measures were weekly measures of mood (mania, depression, and anxiety) and changes in targeted imagery. In addition, daily mood measures were collected using a smart phone text messaging to accurately measure mood variability. Result showed that patients reported an increase in mood stability, as well as improvements on weekly, and pre- and post-measures of mood and target imagery. Moreover, it is important to note that this study concluded that daily measurements were feasible. All in all, ImCT appears promising for bipolar disorder and invites further evaluation.

In the present research proposal, we elaborate on the previous ImCT pilot study (Holmes et al., 2016), comparing its effectiveness in patients with bipolar disorder to psychoeducation treatment. As noted before psychoeducation treatment is one of the most regularly applied psychological intervention for bipolar disorder. In advance of a large upcoming RCT in the UK it is necessary to derive more precise estimates of retention rates, especially on daily monitoring, and information on general feasibility as well as first data comparing ImCT to an appropriate control condition. We propose a randomised controlled feasibility study, comparing the effects of ImCT to psychoeducation in patients suffering from bipolar disorder in patients who standard have regular appointments with their psychiatrist, prescribing, monitoring and adjusting mood stabilising medication in a specialized bipolar treatment centre.

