2. OBJECTIVES

Primary Objective and secondary objectives:

The present research project elaborates on a pilot study by Holmes and colleagues (2016) and an audit (Hales et al., 2018) using a new cognitive behavioural therapy enhanced with imagery techniques (ImCT), with an aim to improve the effectiveness of CBT for patients suffering from bipolar disorder. The pilot study (Holmes et al., 2016) found promising treatment effects but a controlled feasibility study is needed to test whether this treatment is more effective than regular treatment. Therefore, this research projects examines the effect of this new ImCT treatment, by comparing this intervention to psychoeducation treatment, one of the most regularly applied psychological intervention for bipolar disorder. The current

study will provide new insights for an upcoming large RCT evaluating the effectiveness of ImCT in the UK.

[figure not shown]
Our primary objective is to estimate the effects of ImCT compared to psychoeducation on mood variability. We hypothesise that (1) mood variability (primary outcome variable) will show stronger decreases in BD patients receiving ImCT at end of the intervention (T2), at follow-up measurement 8 weeks after concluding the interventions (T3) and at follow-up measurement 16 weeks after concluding the interventions (T4) than psychoeducation. Additionally, the effects of both treatments separately are also compared to baseline period preceding both treatments.

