4.4 Sample size calculation

To estimate the sample size needed for the between group design of this study, we used the study's primary outcome variable, mood variability, which is measured using the Affect Lability Scale (ALS-18).

The primary outcome variable for the between subjects design of the study, is the ALS-18, which was used in the audit (Hales et al., 2018) and in the pilot study by Holmes (Holmes et al., 2016). The effect sizes they found using the ALS-18 were $d = 0.8$ and $d = 0.99$ (see Table 1 below). We expect similar effect sizes in our study, that is $d = 0.9$ (the mean of the prior mentioned studies). Studies on the effect of psychoeducation have shown only moderate effects on medication adherence, knowledge of bipolar disorder and attitudes, but no or limited effect on mood variability or relapse, ranging from no effect (Bond & Anderson, 2015; Kurdal, Tanriverdi, & Savas, 2014) to a minimal effect (maximum of $d = 0.3$, but only in patients with less than 7 episodes), (Gumus, Buzlu, & Cakir, 2015; Morriss et al., 2016). We therefore expect an effect size of $d = 0.6$ (i.e., $d = 0.9$ minus $d = 0.3$). Based on prior mentioned effects of the ALS-18 we calculated the sample size needed, to power this study at 80% to detect an effect size of Cohen's $d = 0.6$ using a significance level of .05 two tailed T-tests using G*power 3.1.9.3 The calculated sample size needed is 45 in each group. The study of Holmes et al. (2016) showed a drop out 1 out of 15. After consulting with the research group from the audit and pilot study we expect a similar drop out rate in the current study. We therefore need a sample size of 48 in each group, 96 in total.

Table 1: Mean (SD) ALS-18 scores before and after ImCT in the pilot study of (Holmes et al., 2016)

Pre-Treatment	End of Treatment	4 week FU	12 week FU	24 week FU	Time	Pairwise differences, Bonferroni corrected pairwise t-test
46.36 (11.26)	35.54 (10.49)	35.43 (10.92)	36.36 (12.58)	34.71 (12.74)	F(4.48)= 6.75, $p < .001$	Pre vs 4w $t(12) = 3.77$, $p = .027$, $d = 0.99$; pre vs 12w

						$t(12)=3.58, p=.038, d = .84$; pre vs 24w $t(12)=4.62, p =.006, d = 0.97$
--	--	--	--	--	--	--

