Where possible multivariate analyses are used to analyse differences between groups, and repeated-measures ANOVA to analyse difference within groups. These will be used to minimise the correlations and dependencies between variables. In order to allow for reliable multivariate analysis, assumptions of sphericity are tested. Multivariate analyses between groups (ImCT, psychoeducation treatment) and repeated-measures ANOVA within groups (T0, T1, T2, T3, T4) are used to determine an omnibus effect. If differences are significant, post hoc analyses (mostly independent T-test) will be used to determine individual differences between groups and between points in time. Bonferoni corrections are used to correct for multiple testing.

Intention-to-treat analyses will constitute the central analyses and completers analyses will be done as supplementary analyses.

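### Formal ALS-18 contrasts between arms at T2, T3 and T4 depend on a significant omnibus test, although the primary objective is to estimate that effect

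*Combined protocol and SAP*

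**What the plan says.** Section 2 states the aim as estimation: "Our primary objective is to estimate the effects of ImCT compared to psychoeducation on mood variability". It follows this with directional hypotheses at the end of treatment (T2) and at 8 and 16 weeks afterwards (T3, T4). Section 1 gives part of the purpose, after retention and general feasibility: "as well as first data comparing ImCT to an appropriate control condition". Section 4.4 says the trial is meant to inform a later RCT of N = 350.

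Section 8 analyses ALS-18 at T0–T4 with a multivariate repeated-measures model, with arm as the between-subjects factor. The multivariate analyses between groups and the repeated-measures ANOVA within groups serve to establish an omnibus effect. The visit-level step is then conditional: "If differences are significant, post hoc analyses (mostly independent T-test) will be used to determine individual differences between groups and between points in time". A Bonferroni correction follows; the number of tests is not given. Section 8 also opens with descriptive means and SDs, which are not conditional on anything, but it does not say that they are given by arm and visit.

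The plan does not state whether the omnibus effect that opens the gate is the time-by-arm interaction or the overall arm effect. It also does not provide for an arm difference with a confidence interval irrespective of significance.

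**The concern.** If the aim is to estimate an effect at three visits, the estimate and its precision should be available however the test comes out. A significance gate works against this in two ways. When the omnibus test fails, the planned analysis stops before the quantity that the objective names. When it passes, the estimates come from a selected set of trials and are on average too large. A non-significant feasibility trial is where the designers of the next trial most need the difference and its interval, because the interval shows which effects remain plausible.

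**Working it through.** **The plan's own figure.** Section 4.4 asks for 80% power at d = 0.6, "using a significance level of .05 two tailed T-tests using G*power 3.1.9.3". The noncentral t calculation gives n = 44.59, rounded up to 45, with power 0.804 at 45. This agrees with "The calculated sample size needed is 45 in each group". Adding 1/15 for drop-out gives 45 × 16/15 = 48, as stated. The figure is right for one ungated t-test; it was not derived for an omnibus test followed by corrected contrasts.

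**Inputs for the gate.** From the documents: 45 analysed per arm, five visits, two-sided 0.05, planned d = 0.6. Assumed, because the documents do not give them: within-person correlation ρ of 0.5 to 0.7, equal between all visits; a true arm difference of zero at T0 and T1 and of d at T2, T3 and T4; and d = 0.3 as an illustration of a smaller effect.

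**Gate A, time-by-arm interaction (Hotelling test).** The noncentrality is (n/2) × [3d² − (3d)²/5]/(1 − ρ) = 22.5 × 1.2d²/(1 − ρ) = 27d²/(1 − ρ), referred to F with 4 and 85 df (critical value 2.479).

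- d = 0.6: 19.44 at ρ = 0.5 and 32.4 at ρ = 0.7
- d = 0.3: 4.86 and 8.1

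**Gate B, arm main effect averaged over T0–T4.** The mean difference is 3d/5 = 0.6d. The SD of a person's mean is √[(1 + 4ρ)/5], which is 0.775 at ρ = 0.5 and 0.872 at ρ = 0.7. The noncentrality is 0.6d × √22.5/SD, referred to t with 88 df.

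- d = 0.6: 2.205 and 1.959
- d = 0.3: 1.102 and 0.979

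The mean T2–T4 arm difference among passing trials comes from simulation, 20,000 trials per setting. Simulated pass rates agree with the exact ones to within 0.004.

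| Gate | True d | ρ | Passes | Contrasts undetermined | Mean difference if passed | Inflation |
|---|---|---|---|---|---|---|
| A | 0.6 | 0.5 | 0.948 | 5% | 0.605 | +1% |
| A | 0.6 | 0.7 | 0.998 | 0.2% | 0.599 | 0% |
| A | 0.3 | 0.5 | 0.366 | 63% | 0.349 | +16% |
| A | 0.3 | 0.7 | 0.584 | 41–42% | 0.323 | +8% |
| B | 0.6 | 0.5 | 0.587 | 41% | 0.706 | +18% |
| B | 0.6 | 0.7 | 0.491 | 51% | 0.746 | +24% |
| B | 0.3 | 0.5 | 0.193 | 81% | 0.526 | +75% |
| B | 0.3 | 0.7 | 0.163 | 84% | 0.564 | +88% |

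Inflation moves by a point or two between simulation runs; for gate A at d = 0.3, runs spanned 7–18%.

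**Sensitivity.** If the correlation decays with distance between visits (AR(1), 0.7), gate A passes 0.858 at d = 0.6 (mean 0.613, +2%) and 0.277 at d = 0.3 (mean 0.371, +24%).

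**A second filter.** If only T2 differences that pass the omnibus test and also a Bonferroni t-test are read (three tests assumed), they average 0.72–0.76 for a true 0.6 and about 0.62–0.64 for a true 0.3.

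**Without the gate.** The expected estimate equals the true d and is available in every trial. The 95% half-width is 1.987 × √(2/45) = 0.42 SD. With the pilot's pre-treatment SD of 11.26 from Table 1, that is 0.42 × 11.26 ≈ 4.7 ALS-18 points.

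**The case against.** The best defence is that little is truly withheld. The repeated-measures model and the descriptive statistics are ungated, and section 10.6 commits to full disclosure of the research data. With means, SDs and numbers by arm and visit, anyone can compute a difference and an interval. So a reader who infers that a non-significant trial would leave no effect estimate at all goes too far. What stands against the defence is that section 8 does not say the descriptive figures are by arm and visit, and an interval that others may work out is not a planned analysis of the primary objective.

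A reader might also infer that the gate more than doubles a true effect of 0.3. The text does not support that for the gate as written: such values, about 0.62–0.65, need the further step of reading only Bonferroni-significant contrasts, and nothing in section 8 says the others go unreported. Under an interaction gate at the planned effect, inflation is close to nil.

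Nor do the documents say that the later RCT will be sized from these contrasts. Its N of 350 is already given, and retention and general feasibility, which this rule does not gate, are among the stated purposes. The d = 0.3 case is likewise illustrative; the 0.3 in section 4.4 is the largest effect expected of psychoeducation, not a between-arm effect.

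Finally, an omnibus test followed by corrected contrasts is a conventional way to test the hypotheses in section 2. That is true, and it can stay for that purpose. It does not serve the estimation aim stated just before them.

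**Conclusion.** The concern holds in this form: the primary objective is estimation, the formal visit-level contrasts are conditional on significance, and no unconditional arm difference with a confidence interval is planned. This conflict rests on the text alone and needs no simulation.

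Its size is not fixed, because the gate is not defined. If it is the time-by-arm interaction, the harm at the planned d = 0.6 is minor, but at a smaller true effect contrasts would often go undetermined, with modest inflation in the rest. If it is the arm main effect, which the wording does not exclude, roughly half of trials would go without contrasts even at d = 0.6, with inflation near one fifth, and both figures are much worse at d = 0.3. All of these rest on 45 per arm, an assumed correlation of 0.5–0.7 that is equal between visits, and a constant effect from T2 to T4. The change is worth making but does not undermine the design or the sample size.

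**What to change.** In section 8, remove the significance condition for the primary outcome. State that the ALS-18 difference, ImCT minus psychoeducation, is reported with its 95% confidence interval at T2, T3 and T4 whatever the omnibus result. Keep the omnibus test and the Bonferroni correction for hypothesis testing only. It would help to name the omnibus effect meant, and to say that means and SDs are tabulated by arm and visit.

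The cost is about two sentences in section 8 and three rows in a results table. No extra patients, assessments or data are needed, and the sample size does not change.

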8. STATISTICAL ANALYSIS

First, descriptive analyses will be used to establish mean scores, standard deviations and to identify outliers. Missing data from our primary outcome variable, will be listwise deleted. In our other outcome variables, data will only be included if pre- and post-measures are completed.

Second, the data will be checked with respect to violation of assumptions (such as error independency, non-normal distributions) for variance-based models.

Primary outcome variable: mood variability:

To assess if there is a stronger decrease in mood variability in the ImCT intervention condition as compared to the psychoeducation condition, multivariate repeated measures analyses are applied. Dependent variables are the scores on the ALS-18 (baseline, T0; pre-treatment, T1; post-treatment, T2; 8-weeks follow-up, T3; 16-weeks follow-up, T4) with treatment condition (ImCT, psychoeducation) as between subjects variable.

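### The post hoc rule does not separate group contrasts from time contrasts and names mostly independent t-tests for both; applied to paired time points, these would overstate the within-arm standard errors

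*Combined protocol and SAP*

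**What the plan says.** All post hoc testing rests on one sentence in section 8 (Statistical analysis). After a significant omnibus result, "post hoc analyses (mostly independent T-test) will be used to determine individual differences between groups and between points in time", with a Bonferroni correction. The number of comparisons to correct for is not given. Section 8 names no paired t-test and no within-patient model contrast.

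The omnibus step in the same paragraph does treat time as within-patient: "repeated-measures ANOVA within groups (T0, T1, T2, T3, T4) are used to determine an omnibus effect". The primary outcome is scored repeatedly in the same people: "Dependent variables are the scores on the ALS-18 (baseline, T0; pre-treatment, T1; post-treatment, T2; 8-weeks follow-up, T3; 16-weeks follow-up, T4").

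Within-arm change is a stated aim. Section 2 (Objectives) says that "the effects of both treatments separately are also compared to baseline period preceding both treatments" for mood variability and repeats this for the symptom and functioning outcomes. Section 3 (Study design) explains that each participant's baseline serves as that person's own control.

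**The concern.** The sentence covers two kinds of contrast. Between arms at one time point the patients differ, and an independent t-test is valid. Between two time points within an arm the patients are the same, and the independent test ignores the correlation between a patient's two scores. When that correlation is positive, the standard error is too large, the confidence interval too wide and the p-value too high.

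At stake is the within-arm comparison with baseline. A real but modest change could be reported as non-significant, and a significant repeated-measures ANOVA could be followed by no significant pairwise difference. The loss would also be uneven. It would hardly touch the large change expected under ImCT but could hide the small change that section 4.4 allows for under psychoeducation, so the two arms' within-arm results could look more different than they are.

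**Working it through.** **Inputs.** Section 4.4, Table 1 (pilot ALS-18, mean (SD)): pre-treatment 46.36 (11.26); end of treatment 35.54 (10.49); 4 weeks 35.43 (10.92); 12 weeks 36.36 (12.58); 24 weeks 34.71 (12.74). Pairwise t(12) against pre-treatment: 3.77, 3.58 and 4.62. Section 4.4 also gives 45 evaluable patients per arm, an expected d of 0.9 for ImCT and at most 0.3 for psychoeducation.

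**Reproducing the pilot figures.** The table column is headed "Pairwise differences, Bonferroni corrected pairwise t-test". Five time points give 5 × 4 / 2 = 10 pairs. Two-sided p-values on 12 df are 0.00267, 0.00378 and 0.00059; times 10, they give .027, .038 and .006, as printed. So the pilot tests were paired, on 13 patients. The printed d of 0.99 is 10.93 / 11.09, where 11.09 is the average of the two SDs, so d is on the raw-SD scale.

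**Standard errors from Table 1.** Paired SE = mean difference / t. Independent SE = sqrt((SD1² + SD2²)/13). The implied rho is (SD1² + SD2² − 13 × SE_paired²) / (2 × SD1 × SD2).

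| Contrast | Difference | Paired SE | Independent SE | Ratio | Implied rho |
|---|---|---|---|---|---|
| Pre vs 4 weeks | 10.93 | 2.90 | 4.35 | 1.50 | 0.56 |
| Pre vs 12 weeks | 10.00 | 2.79 | 4.68 | 1.68 | 0.65 |
| Pre vs 24 weeks | 11.65 | 2.52 | 4.72 | 1.87 | 0.72 |

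Section 1 gives 14 pilot patients; with n = 14 the ratios are about 1.45, 1.61 and 1.80.

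**How firm the range is.** With equal SDs the ratio is 1/sqrt(1 − rho): 1.20 at rho 0.3, 1.41 at 0.5, 1.58 at 0.6, 1.83 at 0.7. Approximate 95% limits (Fisher z, 13 pairs) on the three implied correlations are 0.01 to 0.85, 0.15 to 0.88 and 0.28 to 0.91, so the ratio could lie anywhere from about 1.0 to 3.2. Table 1 gives no t for pre-treatment against end of treatment, the analogue of T1 against T2. If it was left out because it missed Bonferroni significance (an assumption; t below 3.43), its paired SE exceeds 10.82 / 3.43 = 3.16. The independent SE is 4.27, so the ratio is below about 1.35 and rho below about 0.45.

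**Effect in this trial.** Assumptions: n = 45 per arm, equal SDs, rho = 0.6, changes in raw-SD units, two-sided tests. The paired test has noncentrality d × sqrt(45) / sqrt(2 × 0.4), which is 2.25 at d = 0.3 and 6.75 at d = 0.9. Power of the independent test comes from simulating paired data and analysing them as two samples.

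| Within-arm change | Alpha | Independent | Paired |
|---|---|---|---|
| 0.3 SD | 0.05 | about 20% | 59.5% |
| 0.3 SD | 0.005 (10 pairs) | about 2% | 26% |
| 0.9 SD | 0.05 | over 99% | over 99% |
| 0.9 SD | 0.005 (10 pairs) | about 98% | over 99% |

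The true type I error of the independent test at nominal 5% is about 0.3%. At rho 0.3 the gap for a 0.3 SD change at alpha 0.05 is smaller: about 25% against 38%.

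**The case against.** The strongest defence is the word *mostly*. It admits other tests, and time contrasts are the natural exception, since the same paragraph uses repeated-measures ANOVA within groups. A competent analyst would probably pair. This stands in part: the text does not commit to an independent test for every time contrast. But it never says where the exception applies, and section 8 offers no paired alternative to turn to.

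Three stronger readings are tempting, and the documents do not support them.

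- *The within-arm standard errors will be 1.5 to 1.9 times too large.* The documents give no correlation for this trial. The range comes from three contrasts in 13 pilot patients and leaves out end of treatment.
- *On the pilot's own data nothing would be significant, so the trial would miss its effects.* With 13 patients, independent tests do give t = 2.51, 2.14 and 2.47 and Bonferroni p = .19, .43 and .21. With the same means and SDs at n = 45, t is 4.67, 3.97 and 4.60, and p × 10 is .0001, .0014 and .0001. All three stay significant.
- *Power falls from 60% to 20%.* This holds only for a 0.3 SD change, before the planned Bonferroni correction. With that correction over 10 pairs, the paired test itself has only about 26%.

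Reach is also limited. The primary objective is the between-arm effect, tested by the multivariate repeated-measures analysis. The daily-mood analysis already takes each participant as their own control. And with positive correlation the error is conservative, so it cannot create a false benefit.

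**Conclusion.** The concern holds in a limited form. The post hoc sentence does not separate group contrasts from time contrasts, and the test that it mostly names is wrong for the latter. The direction of the error is certain for any positive within-patient correlation. Its size is not: about 1.2 at rho 0.3, 1.4 at rho 0.5, and 1.5 to 1.9 only if the pilot's follow-up correlations carry over.

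Only the within-arm post hoc time contrasts are affected. Between-arm t-tests at a single time point, the omnibus tests, the primary analysis and the 45 per group are not. The practical loss falls on small within-arm changes. The power figures assume rho = 0.6, a Bonferroni family of 10 pairs as in the pilot, and that the 0.3 in section 4.4 can be read as a pre-post change; subtracting it from the pilot's pre-post 0.9 implies that reading. Wrong as written, minor severity.

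**What to change.** Split the sentence in section 8 by type of contrast. For example:

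*After a significant omnibus effect, differences between arms will be tested with independent t-tests. Differences between time points within an arm will be tested with paired t-tests, or with within-patient contrasts from the repeated-measures model. Bonferroni corrections apply to both, over a stated number of comparisons.*

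The between-arm tests need no change on this ground. The cost is one reworded sentence, notified as an amendment under section 10.3 if approval has already been given. It needs no extra patients, measurements or design change. Made before the data are seen, it also removes the choice of test that *mostly* leaves open.

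### Holm's step-down would recover some power that plain Bonferroni gives up on the T2, T3 and T4 contrasts, at the same 5% family-wise level: a cheap improvement, not an error

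*Combined protocol and SAP*

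**What the plan says.** Section 8 (Statistical analysis) plans an omnibus test and, if it is significant, post hoc comparisons, mostly independent t-tests, both between arms and between time points. It then states: "Bonferoni corrections are used to correct for multiple testing". No step-down, hierarchical or closed procedure is named, and the number of tests sharing the correction is not given.

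Hypothesis 1 in section 2 (Objectives) expects a larger fall in mood variability under ImCT "at end of the intervention (T2), at follow-up measurement 8 weeks after concluding the interventions (T3"), and again 16 weeks after the intervention (T4). No visit is singled out. Hypotheses 2a and 2b use the same three times.

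Section 4.4 sizes the trial on one comparison, "using a significance level of .05 two tailed T-tests". The result is "The calculated sample size needed is 45 in each group", raised for dropout to 48 per group. The effect of d = 0.6 is not assigned to any visit, and no correlation between visits is given.

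**The concern.** Single-step Bonferroni holds every contrast to the strictest threshold even after others have been rejected. Holm relaxes the threshold after each rejection and still controls the family-wise error under any dependence between the tests. It needs no visit ordering, no extra assumption and no more patients. Its advantage is largest when several effects are real together, which is the pattern hypothesis 1 predicts. If that pattern is true, the planned correction makes it more likely that the trial misses an effect at one of its three stated times. The visit-specific results are meant to inform a larger trial.

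**Working it through.** **Inputs from section 4.4.** d = 0.6, two-sided α = .05, power 80%, 45 evaluable per arm, dropout 1/15, 48 randomised per arm.

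**Assumed, because the plan does not say.** The family is the three between-group contrasts at T2, T3 and T4; d = 0.6 applies at each; visits are equally correlated, with values from 0 to 0.9 shown.

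**The plan's own figure.** The noncentral-t calculation for d = 0.6, α = .05 and 80% power gives 44.6, so 45 per arm, as stated. At 45 per arm the noncentrality is d√(n/2) = 0.6 × √22.5 = 2.85 on 88 degrees of freedom, and power is 80.4%. The dropout step reproduces as 45 × (1 + 1/15) = 48.

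**Bonferroni, one visit.** The threshold is .05/3 = .0167. The same calculation gives 65.7%. Restoring 80% at that threshold would take 60 per arm (59.6 rounded up).

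**Holm.** Order the three p-values. Compare the smallest with .05/3, the next with .05/2 and the largest with .05, stopping at the first failure. Power was simulated with 100,000 trials per setting (normal outcomes, one t-test per visit). All entries are percentages.

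| Correlation | Per visit: Bonferroni | Per visit: Holm | All three: Bonferroni | All three: Holm | At least one: both |
|---|---|---|---|---|---|
| 0 | 65.8 | 75.3 | 28.5 | 50.0 | 96.1 |
| 0.3 | 65.7 | 74.3 | 36.0 | 55.4 | 91.3 |
| 0.5 | 66.0 | 74.0 | 41.7 | 59.6 | 87.8 |
| 0.7 | 65.7 | 72.9 | 47.3 | 63.6 | 82.6 |
| 0.9 | 65.5 | 71.5 | 55.3 | 68.3 | 75.5 |

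The simulated Bonferroni column agrees with the exact 65.7%. Power for at least one visit is identical because Holm's first step is the Bonferroni step.

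**Sensitivity to the assumptions** (Bonferroni against Holm):

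- Five between-group tests, T0 and T1 included with no difference there: at correlation 0.5, 58.7% against 62.5% per visit and 33.4% against 41.3% for all of T2 to T4; at 0.7, 58.7% against 62.3% and 39.4% against 47.1%.
- Effect at one visit only (correlation 0.5): 65.6% against 65.7%, no gain.
- Effect at two of three visits (0.5): 65.6% against 68.9% per visit.
- Fading effect, d = 0.6, 0.45, 0.3 (0.5): 39.9% against 45.5% averaged over visits; 10.2% against 20.4% for all three.
- Omnibus test required first, using a Hotelling T² test on the three visits as a stand-in: at 0.5, 64.3% against 71.9% per visit and 41.7% against 59.4% for all three; at 0.7, 62.2% against 68.0% and 47.2% against 61.2%.

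**Family-wise error** (three tests, correlation 0.5). No effect anywhere: 4.4% for both. Effect at one visit: 3.2% against 4.1%. Effect at two visits: 1.7% against 3.7%.

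**The case against.** Bonferroni is valid and contradicts nothing else in the plan, so choosing Holm is a preference for efficiency. That stands.

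The family of three is an assumption. Section 8 applies the correction to comparisons between arms and between time points, and the primary model covers T0 to T4. With five between-group tests the gain roughly halves, and adding time-point contrasts could enlarge the family further. This also stands, and it means that defining the family is part of the change. At correlation 0.5, going from Bonferroni over five tests (about 59% per visit) to Holm over three (74%) gains about 15 points. About 7 of these come from narrowing the family (59% to 66%) and 8 from Holm (66% to 74%).

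If hypothesis 1 were one joint claim needing all three visits, each could be tested at .05 with no correction. All-three power would then be 61.7% at correlation 0.5 and 66.1% at 0.7, slightly above Holm. The documents do not define success that way.

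The primary objective is worded as estimation, in a feasibility trial, and Bonferroni comes with simple matching simultaneous intervals. This is a real cost of switching. Against it, the plan does specify significance tests and powers the trial at 80% for one.

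**Conclusion.** The point holds as an optional improvement. That Holm rejects at least as much as Bonferroni at the same family-wise level is a mathematical fact and needs no undocumented input. The size of the gain does. With three contrasts, d = 0.6 at each visit and correlation 0.5 to 0.7, it is about 7 to 8 points at a given visit and 16 to 18 points for all three. With five contrasts it is about 4 and 8 points.

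A reader might infer three stronger things that the documents do not support:

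- *That the plan's correction is wrong.* It is not: it controls the error it is meant to control.
- *That Holm leaves actual error unchanged.* The two match only when no effect exists. When some effects are real, Holm uses error that Bonferroni leaves unspent (3.7% against 1.7% with effects at two of three visits), though it stays below 5% in every setting examined.
- *That Holm restores the planned power.* Power at a given visit remains about 72 to 75% across the correlations shown, because section 4.4 sizes the trial on one unadjusted test. That is a separate matter.

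**What to change.** Before any outcome data are seen, replace the correction sentence in section 8 with:

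> Within each outcome, the between-group contrasts at T2, T3 and T4 form one family and are tested with the Holm step-down procedure at two-sided family-wise .05; the within-group time-point contrasts form a separate family, also tested with Holm.

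The cost is a short amendment and no extra patients. It is more than a change of method name, because it settles a family that the plan leaves open. The 5% level then applies within each family, not across both families or across outcomes.

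The downside is the loss of simple simultaneous intervals that match the tests. Report 95% intervals labelled as unadjusted beside the Holm-adjusted p-values, and note that such an interval can exclude zero when the Holm test is not significant.
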